Study Title: Movement and Music Intervention for Dementia

NCT Number: NCT03121950

Date of document: September 8, 2017

Movement and Music Intervention for Dementia [name], [name], [name]

Dementia impacts 5%-7% of individuals >60 years old.[1] It impacts the individual's ability to perform work, care for him/herself and ultimately leads to physical disability. There is a high caregiver burden associated with dementia and many individuals end their lives in a long-term care facility. Overall caring for individuals with dementia is a psychological, physical and financial burden on their loved ones and society. Average total cost of care per person with dementia (\$287 038) is greater than that of person's with cancer (\$173 383).[2] Although Medicare expenditures were similar across groups, average out-of-pocket spending for patients with dementia (\$61 522) was 81% higher than that for individuals without dementia (\$34 068).[2]

Best care for individuals with dementia currently involves the use of cholinesterase inhibitors to slow cognitive decline. There is no curative therapy and most treatments are implemented to manage behavioral symptoms. There is evidence in both animal and human studies that exercise modifies metabolic, structural and functional dimensions of the brain, even in older adults.[3] Emerging evidence points to a protective effect of exercise on cognitive function in those with mild to moderate dementia but studies are limited in design and scope and while some show benefit others show no impact of exercise on cognition.[3, 4]

Neuroplasticity requires that the correct type and dosage of exercise be applied. Research to date has demonstrated that individuals with mild to moderate dementia retain the ability to undergo neuroplasticity but the type of exercise and dosage needed are not yet clear. Studies have shown that exercise in individuals with dementia can lead to improved balance[5], strength and aerobics[6, 7] and function[4-6]. Studies showing improved cognitive function included a combination of exercise and an activity that was cognitively challenging.[4, 5, 8] Cheng et al. (2014) demonstrated cognitive improvement through the use of a cognitively challenging game, Mahjong.[9] In their study the group who participated in Tai Chi 3 times a week for 12 weeks did not have a slower rate of global deterioration.[9] Two studies demonstrate that optimal benefit may be obtained through the use of an exercise intervention that includes cognitively challenging activities. Law et al. (2014) had individuals with mild cognitive impairment participate in functional task training or in cognitive training alone.[4] Both groups demonstrated improved cognitive function but only the functional task training group improved in functional status and everyday problem solving activities.[4] Lam et al. (2015) compared exercise, cognitive activity or both to demonstrate that the use of both exercise and cognitive training is superior to either one alone.[8]

It is recommended that exercise programs be structured, individualized, higher intensity, longer duration and multicomponent to bring about improvement in cognitive

PROTOCOL IRB Protocol Number: 2016H0211

IRB Approval date: 04/05/2017

function in those with dementia.[3] Due to the current reimbursement market in the insurance industry individualized programs are only feasible for a short duration unless the individual can pay out of pocket for the program. Compliance can be an issue with higher intensity, longer duration programs as demonstrated by the Lam et al. study in which 25% of the participants dropped out before the one year intervention ended.[8] This study included one hour of exercise 3 times a week for a year which was effective but a 25% drop out rate is concerning. The other studies demonstrating improvement in cognitive performance in individuals with dementia ranged from 6 – 48 sessions.[4, 5, 9] Exercise session length was typically 60 minutes.

Dance is increasingly becoming a popular form of exercise intervention for individuals with Parkinson disease (PD)[10-12] and dementia[13-16]. Dance is an aerobic exercise that challenges balance and involves functional transitions. In addition learning dance sequences is cognitively challenging. Dance is a structured, multicomponent exercise that can be higher intensity and thus fulfills the criteria laid out by Kirk-Sanchez et al. (2014) of qualities of an exercise program likely to bring about change in cognitive function.[3] In individuals with Parkinson disease and dementia it has been shown to improve motor function.[10-12, 14-16] In individuals with PD studies have shown improvement in cognitive function as measured by MoCA[11, 12], the Brooks spatial task[12], reverse corsi block test of working memory,[12], frontal assessment battery at bedside and mental rotation task[10]. The only study examining impact of dance on cognition in individuals with dementia showed slight improvement in mini-mental status exam scores.[16]

Music is an integral part of dancing and as such its impact on cognitive and behavioral function must be considered. Studies show that listening to music activates specific areas of the brain, most associated with emotional behaviors.[17] Areas activated are the insular and cingulate cortex, hypothalamus, hippocampus, amygdala and prefrontal cortex.[17] Listening to music has been shown to impact behavior and evoke reminiscing in individuals with dementia.[18] Given its potential impact on neural function we propose to include a control group who will listen to live music performances in a group setting. The control group is proposed to elucidate potential benefits of group socialization and music and differentiate these from the potential benefits of the dance training.

We hypothesize that a structured dance program involving novelty and learning of sequences will improve both motor and cognitive function in individuals with mild to moderate dementia greater than a control intervention of social music listening. Aims of this study are to investigate the impact of dance training on 1.) Functional movements such as sit to stand transfers and walking; 2.) Balance; and 3.) Cognitive function in individuals with mild to moderate dementia.

METHODS

Ninety individuals with a diagnosis of mild to moderate dementia will be recruited to take part in the study. Participants will be equally distributed into a dance training group or a

control group who will listen to music in a group setting. Group placement will alternate

unless the participant expresses a strong preference to be in a specific group.

Inclusion Criteria	Exclusion Criteria	
Diagnosis of dementia (mild to moderate) MMSE equivalent score ≥ 10	Unable to walk 10 feet unassisted	
Age > 60 years old	Presence of orthopedic disorder that impacts walking	
Able to follow simple instructions	Presence of other neurologic diagnosis that impacts cognitive or motor function such as stroke, Parkinson disease or traumatic brain injury	

Enrollment

Participants will be recruited from local neurology clinics, support groups and senior living communities. Potential participants will be told about the study and screened to determine if he/she meets inclusion/exclusion criteria using the screening form administered by a researcher. After screening the participant will be consented and then given the Mini Mental State Exam Equivalent (MMSE equivalent). Individuals with a score < 10 (severe dementia) will be disqualified and will not continue in the study.

Outcome Assessment:

Participants will be recruited and enrolled until there are 15 participants completed in each group. Baseline measures will be assessed by a trained assessor prior to start of the intervention (0-2 weeks), intermediate assessment at 6 weeks and post-intervention assessment 0-2 weeks after completing the intervention. Assessment will take 60 minutes and will be conducted either at a senior living community center, or at the MEND laboratory in Atwell Hall, Ohio State University.

Primary Outcome Measures

Motor: Timed up and Go cognitive

The timed up and go cognitive assesses the ability to stand up, walk, turn and sit back down while doing a cognitive task. The individual is timed first while doing the task without a secondary cognitive task and then while doing the task and counting backwards from 100 in increments of 3. It is valid and reliable measure of mobility and dual task ability.[19]

Cognitive: MoCA

PROTOCOL IRB Protocol Number: 2016H0211

IRB Approval date: 04/05/2017

The Montreal cognitive assessment is a valid and reliable screening tool for dementia that assesses the major cognitive domains. [20] It is a paper test that takes 5 to 10 minutes to administer.

Secondary Outcome Measures

- Balance miniBESTest
 The mini BESTest is a clinical balance assessment tool that aims to target and identify 6 different balance control systems that has been shown to be valid and reliable in the elderly[21]. It takes 10 15 minutes to administer and involves tests static and dynamic balance and includes the TUG cognitive.
- Activities and Function Functional Rating Scale of Symptoms of Dementia (care partner fills out)
 - A scale in which the caregiver rates the ability of the individual with dementia to perform daily care activities, memory and sleep.[22]
- Caregiver burden Caregiver Burden Scale
 - A survey tool that is a valid and reliable measure to assess perceived burden among people caring for others with disabilities.[23]

Intervention:

The dance class will be a 90 minute group class held 2 times per week for 12 weeks. Class will consist of seated warm up and stretching routines followed by seated dance that becomes progressively more challenging and leads into standing dance activities. Each participant will stand behind their chair so that the chair can be used to assist with balance. Dance activities initially comprise simple one step moves and progress to more complex sequences. Sequences will be carried over session to session to promote learning of longer sequences. The dance class will be taught by a trained dance instructor who has experience in teaching dance to individuals with neurodegenerative diseases.

The control group will meet one time per week for 90 minutes and will listen to live music performances. These performances are held in the community room of a local senior care living facility and include residents of the senior care community. Control participants will attend with their caregivers and will have opportunity to socialize with other study participants as well as members of the senior care community. Music style and type varies week to week and is chosen to be appropriate to individuals over 65 years of age.

Statistical Analysis:

We calculated the number needed based on previous studies and arrived at 15 per group. Given there is an expectation that some subjects will be found to not meet the

inclusion criteria when given the mini mental status exam equivalent after consenting and that some individuals may drop out we are asking for permission to enroll a maximum of 45 participants in each group. Once each group has 15 individuals actively participating we will stop enrollment

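### Group placement alternates but yields to a participant's strong preference, so the dance-versus-music comparison can be confounded by who chose each group

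*Combined protocol and SAP*

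**What the plan says.** Under METHODS the two groups are meant to be of equal size: "Participants will be equally distributed into a dance training group or a" music-listening control. The rule for reaching this is "Group placement will alternate", followed at once by the exception "unless the participant expresses a strong preference to be in a specific group". The plan describes no random sequence and no concealment of the next placement. It states no limit on preference placements, no record of them and no separate analysis.

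The paragraphs just before METHODS set out a comparative aim. The control group is there to identify the benefits of music and company and to "differentiate these from the potential benefits of the dance training". The hypothesis is that dance "will improve both motor and cognitive function in individuals with mild to moderate dementia greater than a control intervention of social music listening".

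Statistical Analysis gives a target of 15 per group and an enrolment maximum of 45 per group. It plans a one-way ANOVA for each outcome, or Kruskal-Wallis where the data call for it, and states no baseline or preference term. Outcome Assessment does collect baseline measures before the intervention starts.

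**The concern.** A claim that dance does better than music listening needs groups that are comparable apart from the intervention. Participants placed by their own preference (choosers, below) may differ in mobility, motivation, rate of decline or caregiver logistics. The programmes differ visibly: dance is an active class twice a week, while music listening is once a week. If such differences also affect the Timed Up and Go cognitive or the MoCA, a difference between groups, or the lack of one, may reflect who chose.

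The equal-distribution statement and the limits per group restrain arm size but not the make-up of the arms. A larger sample estimates the same biased difference more precisely. If preference placements go unrecorded, nobody can later judge how much they mattered.

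**Working it through.** **The plan's own figure.** The 15 per group cannot be reproduced, because no effect size, SD, power or sidedness is given. For orientation, a two-sided 5% t-test with 15 per group has 80% power for a difference of 1.06 SD.

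**Inputs from the plan.** 15 per group; two groups; one-way ANOVA (with two groups, the same as a t-test); alpha 0.05.

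**Assumed, because the plan does not give them.** Two-sided test; no true effect; pre-post correlation r = 0.7; a share f of each arm are choosers, split evenly between the arms; and a gap g, the difference between dance-choosers and music-choosers, so that each chooser is shifted by g/2. These are scenarios, not bounds.

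**Formula.** Bias = f × g. The false-positive rate is the chance that a noncentral t with 28 degrees of freedom and noncentrality (bias/SD) × √(15/2) exceeds the two-sided 5% limit. SD is 1 for post values and √(2(1 − 0.7)) = √0.6 = 0.775 for change scores. The plan does not say which of these is tested, so both are shown.

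| Analysis | Gap | f | Bias (SD) | False-positive rate |
|---|---|---|---|---|
| Post values | level, 0.5 | 20% | 0.10 | 5.8% |
| Post values | level, 0.5 | 1/3 | 0.167 | 7.3% |
| Post values | level, 1.0 | 1/3 | 0.333 | 14.3% |
| Post values | level, 1.0 | 50% | 0.50 | 26.2% |
| Change | level only | any of these | 0 | about 5% |
| Change | trajectory, 0.25 | 20%, 1/3, 50% | 0.05, 0.083, 0.125 | 5.3%, 5.9%, 7.1% |
| Change | trajectory, 0.5 | 20%, 1/3, 50% | 0.10, 0.167, 0.25 | 6.3%, 8.8%, 13.7% |

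**Simulation.** The four post-value cases give 5.7%, 7.2%, 13.1% and 23.9%. The simulation filled each arm to 15 and turned away a chooser whose arm was full. That rule is an assumption, not in the plan. Kruskal-Wallis gives 5.7%, 7.1%, 12.6% and 23.0%.

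**Correlation.** For a trajectory gap of 0.5 SD and one third choosers, r = 0.5 gives 7.3% and r = 0.85 gives 12.7%.

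**Baseline adjustment.** For a level gap, the remaining bias is f × g × (1 − r): from 0.2 × 0.5 × 0.3 = 0.03 SD to 0.5 × 1.0 × 0.3 = 0.15 SD. The simulated rate is 5.1% to 7.7%. A trajectory gap unrelated to baseline is not removed.

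**Preference for dance only.** If all choosers want dance and the arms stay equal in size, choosers form 2p/(1 + p) of the dance arm, where p is their share of all comers. That is 33%, 50% and 67% at p = 20%, one third and half. With the same shift per chooser as above:
- Post values, 0.5 SD each: bias 0.25 and 0.33 SD, rates about 10% and 14%, at p = one third and half.
- Change scores, 0.25 SD each: about 6%, 7% and 9%.

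**Sample size.** At 45 per group, biases of 0.10 and 0.50 SD give 7.6% and 65.0%, against 5.8% and 26.2% at 15.

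**The case against.** Several points on the other side have weight.

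- The largest rates need post values to be tested without baseline. The hypothesis speaks of improvement and baseline is collected, so change scores may be the more natural reading. A constant level gap then does no harm, and only a difference in trajectory over the 12 weeks matters. This stands, and is why the range starts near 5%. But the plan does not commit to change scores.
- The word strong may keep overrides few. That is possible, but the plan neither defines it nor counts such placements.
- That choosers count toward the 15 and enter the same test is an inference from silence. It is the ordinary reading, since no other handling is described.
- Baseline data could be used. They would help with a level gap, but the analysis section does not call for them, and they cannot be relied on to remove unmeasured differences.

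A reader might also infer more than the documents support:

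- **That randomisation was promised and broken.** The plan never calls the trial randomised.
- **That the bias favours dance.** Nothing in the plan says who would choose which group.
- **That staff openly know or steer the next placement.** The plan does not say so. Strict alternation is predictable, but its own effect is not quantified here; every figure above concerns preference.

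**Conclusion.** The weakness is real and should be fixed. The placement rule lets self-selection into the comparison on which the hypothesis rests, and nothing else in the plan offsets it. Confidence is high that the weakness exists, but not about its size, because the share of choosers, their prognostic gap and the correlation are all assumed.

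Under the even-split scenarios, the nominal 5% rate becomes about 6% to 26% on post values and about 5% to 14% on change scores with a trajectory gap. After baseline adjustment for a level gap it is about 5% to 8%. These figures show that the problem can range from negligible to serious; they do not estimate this trial's error rate.

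**What to change.** **Minimum, which must be done:**
- Replace alternation with a concealed, computer-generated 1:1 permuted-block list for everyone without a strong preference.
- After consent, the MMSE-equivalent screen and baseline assessment, and before any assignment is revealed, ask for and record any strong preference.
- Use the baseline score as a covariate in the between-group analysis.
- Report the comparison without preference-placed participants.
- If preference placements stay in the main comparison, describe it as non-randomised. This lowers the claim rather than protecting it.

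**Preferred:** report preference-placed participants as a separate descriptive cohort that does not count toward 15 per group, and state whether they use places under the maximum of 45 per group.

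**Cost.** A protocol amendment, a randomisation list and slower recruitment. Filling 30 randomised places takes 30/(1 − p) eligible people: about 38, 45 or 60 at 20%, one third or half choosers.

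Replacing dropouts raises this. An assumed 10% to 25% dropout gives 42 to 50, 50 to 60, or 67 to 80. The 25% is the background section's figure for a one-year study, not for this trial. Whether dropouts are replaced depends on which stopping rule applies, "Participants will be recruited and enrolled until there are 15 participants completed in each group" or "Once each group has 15 individuals actively participating we will stop enrollment"; the two must be reconciled.

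All these counts are below 90 (2 × 45), but people who fail the MMSE-equivalent after consent come on top. At 80, only 10 places would remain for them if the preference cohort also uses places.

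Two further costs follow. A comparison limited to people without a strong preference applies only to such people. And if the preference rule is kept at 15 per group, an even split leaves about 12, 10 or 7 to 8 per group without choosers. Power for an assumed 1.0 SD effect then falls from 75% to about 65%, 56% or 43%.

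### The eligibility table has no exclusion for a known medical contraindication to exercise, although entrants over 60 may be placed in 24 ninety-minute dance classes

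*Combined protocol and SAP*

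**What the plan says.** The eligibility table in the Methods section has three inclusion entries and three exclusion entries.

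- **Inclusion:** "Diagnosis of dementia (mild to moderate) MMSE equivalent score ≥ 10"; "Age > 60 years old", with no upper limit; and an ability to follow simple directions.
- **Exclusion:** inability to walk 10 feet without help; "Presence of orthopedic disorder that impacts walking"; and another neurologic diagnosis affecting cognition or movement.

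The Enrollment section says that candidates are "screened to determine if he/she meets inclusion/exclusion criteria using the screening form administered by a researcher". It then sets the order: "After screening the participant will be consented and then given the Mini Mental State Exam Equivalent". Groups are filled by alternation unless a participant strongly prefers one of them.

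The Intervention section says: "The dance class will be a 90 minute group class held 2 times per week for 12 weeks". Classes open with seated warm-up and stretching and move to "seated dance that becomes progressively more challenging and leads into standing dance activities". Each participant has a chair for support, and the instructor has experience with neurodegenerative disease.

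**The concern.** The background section justifies dance as aerobic exercise that challenges balance and can reach higher intensity. A plan that relies on physical demand for its benefit would normally ask, before entry, whether the participant has been told not to exercise. The table does not ask. Its two health-related exclusions are narrow: the orthopedic entry applies only if walking is affected, and the neurologic entry only if cognition or motor function is affected. A person with, for example, unstable heart disease who can walk 10 feet meets every criterion.

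Three features of this trial make a written item more useful than usual:

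- Participants have mild to moderate dementia and may not reliably volunteer their medical history.
- Recruitment includes support groups and senior living communities as well as neurology clinics, so a treating clinician need not be involved.
- Because placement is by alternation or preference, being eligible for the trial means being eligible for dance.

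What is at stake is the safety of individual participants, not the validity of the comparison.

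**Working it through.** The check is mainly a reading of the text. The plan gives no figure of its own to reproduce on this point.

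**Step 1. Does any criterion cover medical fitness for exercise?**

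| Entry in the table | Type | General medical contraindication covered? |
|---|---|---|
| Mild to moderate dementia, MMSE equivalent of at least 10 | Inclusion | No |
| Age over 60 | Inclusion | No |
| Follows simple directions | Inclusion | No |
| Cannot walk 10 feet without help | Exclusion | No, mobility only |
| Orthopedic disorder | Exclusion | No, and only if walking is affected |
| Other neurologic diagnosis | Exclusion | No, and only if cognition or motor function is affected |

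Count: 3 inclusion + 3 exclusion = 6 entries, of which 0 address medical fitness for exercise.

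**Step 2. Does another section fill the gap?** Enrollment describes the screening form only as a check on the listed criteria, administered by a researcher. Outcome Assessment, Intervention and Statistical Analysis contain no medical clearance, clinician approval or pre-exercise health question.

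**Step 3. What is such a person scheduled for?** From the Intervention section:

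- Classes: 2 per week × 12 weeks = 24.
- Time: 24 × 90 min = 2,160 min; 2,160 / 60 = 36 hours.

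This is scheduled class time, not exertion. It includes seated warm-up, stretching and seated dance, and the protocol does not state an intensity.

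**Step 4. Would an added exclusion use up enrolment places?** The order under Enrollment is screening form, then consent, then MMSE equivalent. Under Statistical Analysis, "we are asking for permission to enroll a maximum of 45 participants in each group" is explained by failures on the MMSE equivalent after consent and by dropout. If places are counted from consent, as that explanation implies, a candidate excluded on the form uses 0 of the 45 places per group. One disqualified on the MMSE equivalent comes after consent and falls within the allowance.

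**What cannot be computed.** The documents give no adverse-event rate and no proportion of candidates with a contraindication. None is assumed here, so the number of people affected is not estimated.

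**The case against.** The strongest objection is that this argues from absence while relevant papers are not available. The screening form is not reproduced and the consent pages were removed from the public file, so either could contain a health question or a warning. That stands as a limit on certainty: the finding is that the protocol does not state such a check, not that none was made. It does not remove the gap, because the form is described only as a check on the table, and the table has no such entry.

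Second, being eligible is not the same as being placed in dance. Candidates are told about the study and give consent, so a person advised against exercise, or the caregiver, could decline or ask for the music group. This narrows the scenario. It is not a safeguard, because it relies on the candidate or caregiver to raise the matter unprompted.

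Third, the class format is cautious: graded progression, chair support and an experienced instructor. The mobility, orthopedic and neurologic exclusions also remove some unsuitable people. These points are fair and reduce the risk, especially of falls and of early overload. But the class measures act after entry, and none of these provisions screens for cardiac or other general medical conditions.

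Fourth, a yes/no item finds only conditions that are already known and reported. It is not clinical clearance, and no section says that a caregiver attends screening. This is true, and it limits the yield of the fix. It does not make the question worthless.

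**Conclusion.** The concern holds as a minor participant-safety point, with medium confidence. None of the six eligibility criteria covers a known medical contraindication to exercise, and nothing else in the protocol does so. Applied as written, the table admits such a person to a programme of 24 classes and 36 scheduled hours.

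The conclusion rests on reading the table and the Enrollment text as complete statements of eligibility. If the screening form already carries a health question, the remaining change is a one-line clarification of the table. The size of the harm is unknown from these documents. The point is not an error in the analysis and should rank below any finding that bears on the validity of the comparison.

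**What to change.** Add one exclusion to the eligibility table: *known medical condition, or clinician advice, that contraindicates participation in exercise*. Add a matching yes/no item to the existing screening form, answered with the caregiver's help where needed, because the form is completed before the MMSE equivalent is given. Apply it identically to every candidate before group placement, including those who prefer music, so that eligibility stays the same in both groups.

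The cost is one table line and one form item, by amendment, with no new visit, test or physician clearance. There are three drawbacks:

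- A few candidates are excluded, including some who could safely have attended the music sessions, and recruitment may take slightly longer.
- One more health question is asked before consent. The increment is small, since the form must already cover orthopedic and neurologic diagnoses.
- Someone must arrange for a caregiver to be available at screening when the candidate cannot answer reliably.

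### The two enrolment stop rules conflict, and under either one people who stop attending have no place in the comparison, so stopping that differs between dance and concert groups can bias the result.

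*Combined protocol and SAP*

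**What the plan says.** The combined protocol and SAP gives two rules for ending enrolment.

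- METHODS, Outcome Assessment: "Participants will be recruited and enrolled until there are 15 participants completed in each group".
- Statistical Analysis: "Once each group has 15 individuals actively participating we will stop enrollment".

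The target comes from the same Statistical Analysis section: "We calculated the number needed based on previous studies and arrived at 15 per group". The ceiling is set partly for attrition. Some people will fail the MMSE-equivalent after consent and, the text continues, "some individuals may drop out we are asking for permission to enroll a maximum of 45 participants in each group".

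On burden, the Intervention section says "The dance class will be a 90 minute group class held 2 times per week for 12 weeks", which is 2 × 12 = 24 sessions that progress from seated to standing sequences. The control group hears live music for 90 minutes once a week; its duration in weeks is not stated. The background remarks that compliance can be a problem in more demanding programmes, and reports that in a cited trial "25% of the participants dropped out before the one year intervention ended", a rate it calls concerning.

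Assessments fall at baseline, at 6 weeks and within two weeks after the intervention. The analysis is a one-way ANOVA, or Kruskal-Wallis, for each outcome. The document names no analysis set, no follow-up of people who stop, no missing-data method and no reporting of dropout by group.

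**The concern.** The first rule counts the target in people who finish. The second counts people taking part at a moment in time. Under the first, someone who stops is replaced. Under the second, someone who stops after enrolment closes is not replaced, and a group may end with fewer than 15 completers. The two rules can therefore give different numbers of participants and of completers.

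Neither rule gives people who stop a place in the comparison. With no follow-up planned for them and a single ANOVA per outcome, the people with post-intervention scores become the comparison set by default. The primary outcomes are mobility under a dual task and cognition, and both plausibly affect whether a person with dementia can stay in a progressing dance class. If people headed for poor scores leave one group more than the other, part of the difference between groups reflects who stayed. Depending on which group loses them, this can create an apparent effect or shrink a real one.

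**Working it through.** **The plan's own figure.** The 15 per group cannot be reproduced, because no effect size, SD or power is given. For scale, a two-sided 5% t-test with 15 per group has 80% power for a standardised difference of 1.06.

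**Inputs.** From the document: 15 completers per group, a ceiling of 45, and 25% dropout in a cited one-year study. Assumed: every other dropout rate, every correlation r between staying and a good outcome, normal outcomes and two-sided testing.

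**Formula.** If the fraction p with the lowest tendency to stay stops, and that tendency correlates r with outcome, the completers' mean rises by r × g(p) SD, where g(p) = φ(z_p)/(1 − p). The bias is the dance value minus the control value; positive favours dance.

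- g(0.10) = 0.1755/0.90 = 0.195
- g(0.25) = 0.3178/0.75 = 0.424
- g(0.30) = 0.3477/0.70 = 0.497
- g(0.40) = 0.3863/0.60 = 0.644

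**No true effect, more stopping in dance.** The false-positive rate comes from the noncentral t with 15 per group.

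| Dance v control dropout | r | Bias (SD) | False positives |
|---|---|---|---|
| 25% v 10% | 0.3 | 0.3 × 0.229 = 0.07 | 5.4% |
| 25% v 10% | 0.5 | 0.5 × 0.229 = 0.11 | 6.1% |
| 25% v 10% | 0.7 | 0.7 × 0.229 = 0.16 | 7.1% |
| 30% v 10% | 0.3 | 0.3 × 0.302 = 0.09 | 5.7% |
| 30% v 10% | 0.7 | 0.7 × 0.302 = 0.21 | 8.6% |

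A simulation of 20,000 trials per scenario, enrolling each group until 15 complete, gave the same biases for 25% v 10% and false-positive rates of 5.5%, 6.3% and 7.6%.

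**Opposite direction.** With 10% stopping in dance and 25% in control, the bias has the same size and the opposite sign. With 10% in dance, 40% in control and r = 0.5, a true 0.5 SD benefit shrinks by 0.5 × (0.644 − 0.195) = 0.22 to 0.28 SD. In simulation the power fell from 26% to 12.5%.

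**Equal rates, different reasons.** If 25% stop in both groups but stopping relates to outcome only in dance (r = 0.5), the bias is 0.5 × 0.424 = 0.21 SD. In simulation the false-positive rate was 8.5%. The bias is nil if the rates and the reasons are both the same, or if stopping is unrelated to outcome.

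**Number to allocate.** 15/(1 − 0.25) = 20 per group. With 25% dropout, the chance that a given group of 20 has fewer than 15 completers is P(X ≤ 14) for Binomial(20, 0.75), which is 38%.

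**The case against.** Several stronger readings are tempting, and the document does not support them.

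- **That replacing dropouts causes the bias.** It does not. The formula has no replacement term, and a fixed allocation analysed on completers alone has the same mean bias. The cause is leaving dropouts out of the comparison; a completer-based target builds that in. Replacing people who fail the MMSE-equivalent is harmless.
- **That the plan states a completer-only ANOVA.** It states no analysis set. The 6-week visit could supply scores for some people who stop. The completer comparison is a strong inference from a target counted in completers and the absence of any other provision.
- **That completion will differ by group.** The text supports only that it may. The 25% comes from a one-year programme held three times a week, whereas this one lasts 12 weeks at two sessions a week. Letting people with a strong preference choose their group may also reduce stopping from dislike of dance.
- **That the damage cannot be repaired in analysis.** Baseline scores are collected, and adjusting for them removes the part of the selection that they explain. The rest stays.
- **That harm is hidden.** The document is silent on reporting reasons for stopping; it does not say they will go unreported.

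It is also fair that the bias at 25% v 10% is modest beside the 1.06 SD that 15 per group can detect with 80% power. What stands is that the stop rules conflict and that nothing in the plan keeps people who stop in the comparison.

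**Conclusion.** The point holds as a design weakness that should be corrected. The plan followed as written leads to a comparison of completers between groups of unequal burden, under two stop rules that disagree. At 25% v 10% dropout the likely distortion is small to moderate. It grows with the imbalance, and it can arise at equal rates when the reasons for stopping differ. These sizes illustrate the risk and do not predict it: they rest on assumed correlations and, apart from the borrowed 25%, on assumed rates. Outcome data never collected on people who stop cannot be obtained afterwards, so the change belongs before or during enrolment.

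**What to change.** 1. Define enrolment by the number allocated per group after passing the MMSE-equivalent, for example 20, which is within the ceiling of 45. Delete both the completer trigger and the actively-participating trigger, and do not replace anyone once allocated.
2. Invite everyone allocated, including those who stop attending, to the scheduled 6-week and post-intervention assessments.
3. Make the primary comparison all allocated participants in their allocated group, using every available score. One option is a repeated-measures model of the baseline, 6-week and post-intervention scores, with missing-at-random stated as its assumption.
4. Show the completer comparison as secondary, and report numbers and reasons for stopping by group.

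The cost is protocol wording, follow-up calls and a dropout table. Expected enrolment hardly changes, because 15 completers at 25% dropout already needs about 20 per group. There are two downsides. Including people who stopped attending somewhat dilutes the estimate. If they do not return for assessment, a given group of 20 has a 38% chance of fewer than 15 completers at 25% dropout; a larger fixed number would lower that risk.

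This does not make the comparison a randomised one. Alternation with a preference override remains a separate source of selection.
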